7. Measurable disease according to Response Evaluation Criteria In Solid Tumours (RECIST) criteria version 1.1.
8. Eastern Cooperative Oncology Group (ECOG) (see Appendix A) performance status (PS) of 0 to 1.
9. Screening laboratory values as follows:
  - a. Absolute neutrophil count (ANC)  $\geq 1,000/\text{mm}^3$  [ $1.0 \times 10^9/\text{L}$ ].
  - b. Platelet count  $\geq 75,000/\text{mm}^3$  [ $75 \times 10^9/\text{L}$ ].

- c. Hemoglobin  $\geq 8.0$  g/dL.
  - d. Total bilirubin  $\leq 2$  x upper normal limit (UNL) [biliary stent allowed]. A subject with an isolated elevation of indirect bilirubin is eligible.
  - e. Aspartate aminotransferase (AST) and alanine aminotransferase (ALT)  $\leq 2.5$  x UNL (5 x UNL in the presence of liver metastases).
  - f. Calculated or measured creatinine clearance  $\geq 30$  mL/min (creatinine clearance measured based on 24-hour urine collection should be considered to help assess eligibility).
  - g. Serum phosphate  $< 1.5$  x UNL.
10. Female subjects of child-bearing potential must have a negative serum pregnancy test (minimum sensitivity of 25 mIU/mL) at screening and be willing to practice the highly effective contraception methods listed below from the time of study entry up to 6 months after the last day of treatment:
- a. Intrauterine device (IUD)
  - b. Intrauterine hormone-releasing system (IUS)
  - c. Bilateral tubal occlusion
  - d. Vasectomized partner
  - e. Sexual abstinence if corresponds to usual and preferred lifestyle of subject.

For hormonal contraceptives see Section 7.7.1.

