8.4 Handling of Unscheduled Assessments or Retests

In case of pre-dose retests, the latest value will be used in the analysis. The post-dose retests and the unscheduled assessments will not be used in the summary statistics but will be used in the derivation of endpoints that are not related to a specific timepoint (i.e. worst-case assessment, BOR, time to event endpoints, etc.). They will also be displayed in listings.

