9 GENERAL STATISTICAL CONSIDERATIONS

9.1 General Conventions

The statistical analysis described below corresponds to analysis planned for the study. Any deviation from the planned analysis will be documented in clinical study report.

Continuous data will be presented in the form of descriptive statistics, as the number of observations, mean, standard deviation, minimum, 25th percentile (Q1), median, 75th percentile (Q3) and maximum.

Categorical data, including ordinal data, will be presented using contingency tables with absolute and relative frequencies. Missing will be considered as a category and included in the calculation of percentages, unless otherwise stated.

For time-to-event endpoints, Kaplan Meier (K-M) estimates will be provided and include number and percentage of events/censored, 25th (Q1), median and 75th (Q3) survival time and associated 95% confidence interval (CI, if applicable), survival rate and 95% CI at pre-specified time points. For the CIs, these will be Brookmeyer-Crowley for the survival time quartiles and Greenwood for the survival rate.

For PK parameters and concentrations, summary statistics in the tabulation will include number of non-missing value, number below the LOQ, mean, standard deviation, Q1, Q3, 90% CI of the arithmetic mean, coefficient of variation (CV%), median, minimum, maximum, geometric mean, 90% CI of the geometric mean, geometric standard deviation [calculated as: $\text{geo standard deviation} = \exp(\text{SDlog})$] and geometric CV% [calculated as: $\text{geo CV\%} = \text{SQRT}(\exp(\text{SDlog}^2) - 1) * 100\%$; where SDlog is the standard deviation of the log-transformed values].

The minimum and maximum will be reported to the same number of decimal places as the raw data recorded in the database. The mean, median, confidence intervals, Q1 and Q3 will be reported to one more decimal place than the raw data recorded in the database. The standard deviation will be reported to two more decimal places than the raw data recorded in the database. Percentages will be reported with one decimal place. The CV% is reported as a percentage with 1 decimal place.

Baseline measurement is the latest value collected prior to the administration of study drug.

All data analyses will be performed using SAS® statistical software version 9.4 or higher, R software version 3.3 or higher and NONMEM®.

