10.3 Safety Analyses

The safety analysis will be conducted in the Safety Population.

After PA2 is in force, safety assessments for on-treatment and off-treatment subjects will be performed using standard institutional practice and using local laboratory testing. Generally, safety data collected by the local investigator at all clinic visits but only AEs, SAE and AESI will be recorded in the eCRF to support the ongoing safety assessments up to 30 days after last administration of study treatment. The changes in study design relating to safety data include:

- Central clinical laboratory will no longer be performed but will use the local laboratory. Central and local laboratory data will be analyzed together, i.e. not separate analysis for each data source. Shifts in central and local laboratory values will be determined based on the central or local reference range, respectively.
- ECGs will not necessarily be collected in triplicate and central reading will not be performed. Local reading of ECGs will be used. Central and local ECG readings will be analyzed together.

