10.3.3 Clinical Laboratory Evaluations

Laboratory parameters include:

- Hematology: Complete blood count with differential, hemoglobin and platelet count.
- Chemistry: Total protein, albumin, indirect and total bilirubin, aspartate aminotransferase, alanine aminotransferase, alkaline phosphatase, electrolytes (sodium, potassium, calcium, and magnesium), serum phosphate, serum creatinine, creatinine clearance, uric acid, bile salts.
- Urinalysis: Red blood cells/hpf, white blood cells/hpf, casts/hpf, protein dipstick test.

For the purposes of summarization in both the tables and listings, all laboratory values will be presented in SI units. Both local and central laboratory values will be included in the analysis.

Hematology and chemistry parameters and corresponding changes from baseline will be presented as descriptive statistics by visit.

Shift tables based on the NCI-CTCAE v5.0 toxicity grading (and ad hoc grading criteria for hyperphosphatemia) will be presented for each hematology and chemistry parameter between baseline and the highest post-baseline NCI-CTCAE v5.0 toxicity grade or the highest post-baseline ad hoc grading criteria for hyperphosphatemia (including unscheduled assessment). The highest toxicity grade can either be above or below the laboratory standard normal range.

For hematology and chemistry parameters without a toxicity grading scale, the shift table will present directional shifts from baseline to above or below the laboratory standard normal range using the maximum increase and/or decrease observed post-baseline. Subjects who experienced both low and high laboratory test results will be reported in a separate “Low and High” column. “Low” and “High” column will represent the subjects having only low/high values respectively.

Boxplots of actual values and change from baseline will be presented by visit for selected hematology and chemistry parameters as relevant. Log transformation will be applied if necessary.

Urinalysis parameters will be summarized by visit using descriptive statistics. For categorical urinalysis parameters, missing data will not be considered as a category and the calculation of frequencies will use the number of non-missing observations. Results from the urinary pregnancy test will be listed.

Summary statistics will be presented for subjects with at least one post-baseline phosphate (phosphorus) level above 5.5:

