Chemistry	Alanine Aminotransferase	Alanine aminotransferase increased	H	U/L	(upcase(bnrind) in ('NORMAL','LOW') and avar <= ULN) or (upcase(bnrind) ='HIGH' and avar <= 1.5*base)	(upcase(bnrind) in ('NORMAL','LOW') and ULN < avar <= 3*ULN) or (upcase(bnrind) ='HIGH' and 1.5*base<avar<=3*base)	(upcase(bnrind) in ('NORMAL','LOW') and 3*ULN < avar <= 5*ULN) or (upcase(bnrind) ='HIGH' and 3*base<avar<= 5*base)	(upcase(bnrind) in ('NORMAL','LOW') and 5*ULN < avar <= 20*ULN) or (upcase(bnrind) ='HIGH' and 5*base<avar<=20*base)	(upcase(bnrind) in ('NORMAL','LOW') and 20*ULN < avar) or (upcase(bnrind) ='HIGH' and 20*base<avar)
Chemistry	Albumin	Hypoalbuminemia	L	g/L	LLN <= avar	30 <= avar < LLN	20 <= avar < 30	avar < 20	

Category	Parameter	CTCAE Term	CTC Grading direction: Hypo (L)/ Hyper (H)/ No Grading (NA)	CTC Lab Test Unit	CTC Grade 0	CTC Grade 1	CTC Grade 2	CTC Grade 3	CTC Grade 4
Chemistry	Alkaline Phosphatase	Alkaline phosphatase increased	H	U/L	(upcase(bnrind) in ('NORMAL','LOW') and aval <= ULN) or (upcase(bnrind) ='HIGH' and aval <= 2*base)	(upcase(bnrind) in ('NORMAL','LOW') and ULN < aval <= 2.5*ULN) or (upcase(bnrind) ='HIGH' and 2*base<aval<=2.5*base)	(upcase(bnrind) in ('NORMAL','LOW') and 2.5*ULN < aval <= 5*ULN) or (upcase(bnrind) ='HIGH' and 2.5*base<aval<= 5*base)	(upcase(bnrind) in ('NORMAL','LOW') and 5*ULN < aval <= 20*ULN) or (upcase(bnrind) ='HIGH' and 5*base<aval<=20*base)	(upcase(bnrind) in ('NORMAL','LOW') and 20*ULN < aval) or (upcase(bnrind) ='HIGH' and 20*base<aval)
Chemistry	Aspartate Aminotransferase	Aspartate aminotransferase increased	H	U/L	(upcase(bnrind) in ('NORMAL','LOW') and aval <= ULN) or (upcase(bnrind) ='HIGH' and aval <= 1.5*base)	(upcase(bnrind) in ('NORMAL','LOW') and ULN < aval <= 3*ULN) or (upcase(bnrind) ='HIGH' and 1.5*base<aval<=3*base)	(upcase(bnrind) in ('NORMAL','LOW') and 3*ULN < aval <= 5*ULN) or (upcase(bnrind) ='HIGH' and 3*base<aval<= 5*base)	(upcase(bnrind) in ('NORMAL','LOW') and 5*ULN < aval <= 20*ULN) or (upcase(bnrind) ='HIGH' and 5*base<aval<=20*base)	(upcase(bnrind) in ('NORMAL','LOW') and 20*ULN < aval) or (upcase(bnrind) ='HIGH' and 20*base<aval)
Chemistry	Calcium Corrected	Hypercalcemia	H	mmol/L	aval <= ULN	ULN < aval <= 2.9	2.9 < aval <= 3.1	3.1 < aval <= 3.4	3.4 < aval
Chemistry	Calcium Corrected	Hypocalcemia	L	mmol/L	LLN <= aval	2 <= aval < LLN	1.75 <= aval < 2	1.5 <= aval < 1.75	aval < 1.5

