Category	Parameter	CTCAE Term	CTC Grading direction: Hypo (L)/ Hyper (H)/ No Grading (NA)	CTC Lab Test Unit	CTC Grade 0	CTC Grade 1	CTC Grade 2	CTC Grade 3	CTC Grade 4
Chemistry	Calcium, Ionized	Hypercalcemia	H	mmol/L	aval <= ULN	ULN < aval <= 1.5	1.5 < aval <= 1.6	1.6 < aval <= 1.8	1.8 < aval
Chemistry	Calcium, Ionized	Hypocalcemia	L	mmol/L	LLN <= aval	1 <= aval < LLN	0.9 <= aval < 1	0.8 <= aval < 0.9	aval < 0.8
Chemistry	Creatinine	Creatinine increased	H	umol/L	aval <= ULN	ULN < aval <= 1.5*ULN	(1.5*ULN < aval <= 3*ULN) or (. < 1.5*BASE < aval <= 3*BASE)	(3*ULN < aval <= 6*ULN) or (. < 3*BASE < aval)	6*ULN < aval
Chemistry	Creatinine Clearance	Chronic kidney disease	L	mL/sec	LLN <= aval	1 <= aval < LLN	0.5 <= aval < 1	0.25 <= aval < 0.5	aval < 0.25
Chemistry	Glomerular Filtration Rate	Chronic kidney disease	L	mL/min/1.73m2	LLN <= aval	60 <= aval < LLN	30 <= aval < 60	15 <= aval < 30	aval < 15
Chemistry	Magnesium	Hypermagnesemia	H	mmol/L	aval <= ULN	ULN < aval <= 1.23		1.23 < aval <= 3.3	3.3 < aval
Chemistry	Magnesium	Hypomagnesemia	L	mmol/L	LLN <= aval	0.5 <= aval < LLN	0.4 <= aval < 0.5	0.3 <= aval < 0.4	aval < 0.3
Chemistry	Phosphorus	Hyperphosphatemia	H	mmol/L	aval <= ULN	ULN < aval < 1.78	1.78 <= aval < 2.26	2.26 <= aval < 3.23	aval >= 3.23
Chemistry	Potassium	Hyperkalemia	H	mmol/L	aval <= ULN	ULN < aval <= 5.5	5.5 < aval <= 6	6 < aval <= 7	7 < aval
Chemistry	Potassium	Hypokalemia	L	mmol/L	LLN <= aval	3 <= aval < LLN		2.5 <= aval < 3	aval < 2.5
Chemistry	Sodium	Hyponatremia	H	mmol/L	aval <= ULN	ULN < aval <= 150	150 < aval <= 155	155 < aval <= 160	160 < aval
Chemistry	Sodium	Hyponatremia	L	mmol/L	LLN <= aval	130 <= aval < LLN	125 <= aval < 130	120 <= aval < 125	aval < 120

Category	Parameter	CTCAE Term	CTC Grading direction: Hypo (L)/ Hyper (H)/ No Grading (NA)	CTC Lab Test Unit	CTC Grade 0	CTC Grade 1	CTC Grade 2	CTC Grade 3	CTC Grade 4
Chemistry	Total Bilirubin	Blood bilirubin increased	H	umol/L	(upcase(bnrind) in ('NORMAL','LOW') and aval <= ULN) or (upcase(bnrind) ='HIGH' and aval <= base)	(upcase(bnrind) in ('NORMAL','LOW') and ULN < aval <= 1.5*ULN) or (upcase(bnrind) ='HIGH' and base<aval<=1.5*base)	(upcase(bnrind) in ('NORMAL','LOW') and 1.5*ULN < aval <= 3*ULN) or (upcase(bnrind) ='HIGH' and 1.5*base<aval<= 3*base)	(upcase(bnrind) in ('NORMAL','LOW') and 3*ULN < aval <= 10*ULN) or (upcase(bnrind) ='HIGH' and 3*base<aval<=10*base)	(upcase(bnrind) in ('NORMAL','LOW') and 10*ULN < aval) or (upcase(bnrind) ='HIGH' and 10*base<aval)

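### In the SAP's shift tables for ALT, AST, ALP and total bilirubin every baseline grade is 0, and ALT rising from 4x to 5.9x ULN is shown as Grade 0 to Grade 0

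*SAP*

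**What the plan says.** SAP 10.3.3 promises, for each graded haematology and chemistry test, a shift table "between baseline and the highest post-baseline NCI-CTCAE v5.0 toxicity grade", with unscheduled samples counted towards the worst grade. The grading table in the same section is the only grading rule given.

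For ALT, AST, ALP and total bilirubin, that table has two branches. Subjects with a normal or low baseline are graded in multiples of ULN. Subjects with a high baseline are graded in multiples of their own baseline: Grade 0 for ALT is "upcase(bnrind) ='HIGH' and avar <= 1.5*base" (AST has the same limit), for ALP it runs to 2x baseline, and for total bilirubin it is "upcase(bnrind) ='HIGH' and aval <= base".

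Creatinine, in the same table, is handled differently. Its ULN limits apply to everyone and a baseline multiple is an additional route to a grade; Grade 2, for example, is "1.5*ULN < aval <= 3*ULN) or (. < 1.5*BASE < aval <= 3*BASE".

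SAP 9.1 defines the reference value: "Baseline measurement is the latest value collected prior to the administration of study drug".

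The protocol expects raised baselines. Inclusion criterion 9e (Section 6.1) allows AST/ALT up to 2.5x the upper limit, or "5 x UNL in the presence of liver metastases"; 9d allows total bilirubin up to 2x. In Section 6.2, exclusion 8 bars toxicities above Grade 1, but 8b and 8c make exceptions for AST/ALT up to 5x ULN with liver metastases and ALP up to 5x ULN with bone metastases.

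**The concern.** A shift table is meant to show where subjects started and where they ended. If the rule can return only Grade 0 at the start, the table cannot separate subjects who entered with raised liver tests from those who entered normal. An ALT that falls from 4x to 0.9x ULN, stays at 4x, or rises to 5.9x lands in the same 0-to-0 cell.

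The post-baseline side also mixes two scales. ALT going from 0.9x to 3.1x ULN is Grade 2, while 4x to 5.9x ULN is Grade 0, and the table does not show which scale a subject was graded on.

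This matters because Protocol 3.3.3 names hepatic disorders among the risks under close monitoring, and because the population includes biliary tract cancer and subjects with liver metastases. Other planned outputs fill the gap only in part. By-visit summaries are in SI units, and under SAP 8.4 "The post-dose retests and the unscheduled assessments will not be used in the summary statistics". Under SAP 10.3, "Central and local laboratory data will be analyzed together", so laboratories with different normal ranges are pooled. By-subject listings show each value, but no planned table sets peak elevation against baseline elevation as multiples of ULN.

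**Working it through.** The plan states no figure to reproduce; the check applies the SAP's limits literally. Inputs are the upper limits of each grade in the SAP 10.3.3 grading table:

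| Test | Branch | Grade 0 up to | Grade 1 up to | Grade 2 up to | Grade 3 up to |
|---|---|---|---|---|---|
| ALT, AST | normal/low, x ULN | 1 | 3 | 5 | 20 |
| ALT, AST | high, x baseline | 1.5 | 3 | 5 | 20 |
| ALP | normal/low, x ULN | 1 | 2.5 | 5 | 20 |
| ALP | high, x baseline | 2 | 2.5 | 5 | 20 |
| Total bilirubin | normal/low, x ULN | 1 | 1.5 | 3 | 10 |
| Total bilirubin | high, x baseline | 1 | 1.5 | 3 | 10 |

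**Step 1: baseline grade.** At baseline, value = baseline.
- Normal or low baseline: value <= ULN, so Grade 0.
- High baseline: value / baseline = 1, and 1 <= 1.5 (ALT, AST), 1 <= 2 (ALP), 1 <= 1 (bilirubin), so Grade 0.

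Over baselines from 0.001x to 30x ULN, the only grade returned was 0 for all four tests. The ULN branch over the same range returns Grades 0 to 4.

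**Step 2: worked shifts** (values in multiples of ULN).

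| Test | Baseline to worst | Ratio to baseline | SAP rule | ULN limits at both times |
|---|---|---|---|---|
| ALT | 4 to 5.9 | 5.9/4 = 1.475 | 0 to 0 | 2 to 3 |
| ALT | 5 to 7.5 | 1.5 | 0 to 0 | 2 to 3 |
| ALT | 2.5 to 3.75 | 1.5 | 0 to 0 | 1 to 2 |
| ALT | 0.9 to 3.1 | not used (normal baseline) | 0 to 2 | 0 to 2 |
| ALP | 5 to 10 | 2 | 0 to 0 | 2 to 3 |
| Bilirubin | 2 to 2 | 1 | 0 to 0 | 2 to 2 |
| Bilirubin | 2 to 4 | 2 | 0 to 2 | 2 to 3 |

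**Step 3: where ULN Grade 3 can be shown as Grade 0.** This needs a value above 5x ULN that is still within the Grade 0 multiple of baseline.
- ALT/AST: baseline above 5/1.5 = 3.33x ULN.
- ALP: baseline above 5/2 = 2.5x ULN.
- Bilirubin: not possible through a rise, because any value above baseline is at least Grade 1.

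**Step 4: limits at the eligibility ceilings for ALT/AST.**

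| Baseline | Grade 0 up to | Grade 3 above | Grade 4 above |
|---|---|---|---|
| 2.5x ULN | 1.5 x 2.5 = 3.75x | 5 x 2.5 = 12.5x | 20 x 2.5 = 50x |
| 5x ULN (liver metastases) | 1.5 x 5 = 7.5x | 5 x 5 = 25x | 20 x 5 = 100x |
| Normal or low (ULN branch) | 1x | 5x | 20x |

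**Step 5: how many subjects.** The documents do not say. Assuming that 10% to 50% of the 63 evaluable subjects at the second IDMC meeting (SAP 10.8.2) had a raised baseline on a given test, 0.10 x 63 = 6.3 and 0.50 x 63 = 31.5, or about 6 to 32 per test.

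**The case against.** The strongest reply is that baseline-relative grading is deliberate. In a single-arm trial with biliary tract cancer, liver metastases and stents, a rise relative to the subject's own baseline separates drug from disease better than an absolute level. On that view a 3.4-fold rise from 0.9x deserves a higher grade than a 1.5-fold rise from 4x, and the ULN limits are a comparator that the SAP does not apply to these subjects. No conflict with CTCAE v5.0 has been shown. This stands as a reason to keep baseline-relative grading after baseline. It does not help a baseline column that can hold only one value.

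Second, the table shells are in a separate document and might grade baseline differently. That is possible, but the SAP gives no other rule and should state one.

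Third, coverage is wider than summaries and listings. Clinically relevant changes go on the AE page and enter the TEAE tables by worst grade; boxplots are planned for selected tests; direct and indirect bilirubin get directional shifts against the normal range. All true, and no individual value is lost. Still, none of these tabulates baseline against peak elevation relative to ULN.

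Fourth, the 6 to 32 range is an assumption about any raised baseline. The headline example needs ALT/AST above 3.33x ULN, which under the entry limits means essentially subjects with liver metastases, and no count for them is available. The 63 is also not the Safety Population. These limits on size stand.

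Fifth, the creatinine conditions overlap with no stated precedence: baseline 1.4x and value 3.5x ULN meets Grade 2 through baseline (3.5/1.4 = 2.5) and Grade 3 through ULN. So the statement that baseline can only raise the creatinine grade assumes the highest matching grade is taken. The baseline creatinine grade is unaffected, because a value cannot exceed 1.5x itself; it rests on ULN alone and is informative.

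**Conclusion.** The concern holds. On the SAP's text, every subject with a baseline value is Grade 0 at baseline in the ALT, AST, ALP and total bilirubin shift tables, and ALT from 4x to 5.9x ULN is tabulated as no shift. The tables cannot show pre-existing elevation, and they show lower grades than the ULN limits would for on-treatment elevation in subjects who entered with raised tests.

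The conclusion assumes that the baseline column uses the grading table in SAP 10.3.3. The number of subjects affected is unknown. The consequence is confined to descriptive safety displays: the dose rules in Protocol Table 5-1 and the efficacy analyses do not change. The change should be made, because hepatic disorders are a named risk and the entry criteria admit the subjects for whom the display fails.

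**What to change.** In SAP 10.3.3, for ALT, AST, ALP and total bilirubin:

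- Add a shift table by cohort in which both the baseline and the worst post-baseline value, unscheduled samples included, are graded on the ULN limits already in the SAP, using the reference range of the laboratory that measured the sample.
- Alternatively or in addition, tabulate peak post-baseline multiple of ULN against baseline multiple of ULN by cohort.
- Keep the baseline-relative grades as a separate table, labelled as such.
- Do not pair a ULN-graded baseline column with baseline-relative post-baseline grades; that would mix the scales again.

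The cost is SAP wording and one or two extra tables from data already collected. The downside is that more subjects will show a non-zero liver grade, some of it due to disease rather than drug, which is why the baseline-relative table should stay alongside.

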### 9.1.3. Severity of Adverse Events

Adverse events will be graded according to the NCI-CTCAE v5.0 criteria.

Hyperphosphatemia, which is not included in the NCI-CTCAE v5.0, will be graded as follows:

1. Serum phosphate levels > ULN but < 5.5 mg/dL (~ equivalent to Grade 1);
2. Serum phosphate levels 5.5 - 6.9 mg/dL (~ equivalent to Grade 2);
3. Serum phosphate levels 7 - 9.9 mg/dL (~ equivalent to Grade 3, as this is the expected level at which soft tissue calcifications might develop);
4. Serum phosphate levels > 10 mg/dL with or without renal impairment (~ equivalent to Grade 4).

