- Time from start of treatment to Phosphate level of 5.5mg/dL or higher, defined as [earliest date where phosphate \geq 5.5mg/dL] – [date of first administration of the study drug] +1

Category	Parameter	CTCAE Term	CTC Grading direction: Hypo (L)/ Hyper (H)/ No Grading (NA)	CTC Lab Test Unit	CTC Grade 0	CTC Grade 1	CTC Grade 2	CTC Grade 3	CTC Grade 4
Hematology	Hemoglobin	Hemoglobin increased	H	g/L	CHG <= 0	0 < CHG <= 20	20 < CHG <= 40	40 < CHG	
Hematology	Hemoglobin	Anemia	L	g/L	LLN <= aval	100 <= aval < LLN	80 <= aval < 100	aval < 80	
Hematology	Leukocytes	Leukocytosis	H	G/L	aval <= 100			100 < aval	
Hematology	Leukocytes	White blood cell decreased	L	G/L	LLN <= aval	3 <= aval < LLN	2 <= aval < 3	1 <= aval < 2	aval < 1
Hematology	Lymphocytes	Lymphocyte count increased	H	G/L	aval <= 4		4 < aval <= 20	20 < aval	
Hematology	Lymphocytes	Lymphocyte count decreased	L	G/L	LLN <= aval	0.8 <= aval < LLN	0.5 <= aval < 0.8	0.2 <= aval < 0.5	aval < 0.2
Hematology	Neutrophils	Neutrophil count decreased	L	G/L	LLN <= aval	1.5 <= aval < LLN	1 <= aval < 1.5	0.5 <= aval < 1	aval < 0.5
Hematology	Platelets	Platelet count decreased	L	G/L	LLN <= aval	75 <= aval < LLN	50 <= aval < 75	25 <= aval < 50	aval < 25
Hematology	Basophils		NA						
Hematology	Basophils/Leukocytes		NA						
Hematology	Eosinophils		NA						
Hematology	Eosinophils/Leukocytes		NA						

Category	Parameter	CTCAE Term	CTC Grading direction: Hypo (L)/ Hyper (H)/ No Grading (NA)	CTC Lab Test Unit	CTC Grade 0	CTC Grade 1	CTC Grade 2	CTC Grade 3	CTC Grade 4
Hematology	Ery. Mean Corpuscular Hemoglobin		NA						
Hematology	Ery. Mean Corpuscular HGB Concentration		NA						
Hematology	Ery. Mean Corpuscular Volume		NA						
Hematology	Erythrocyte Cell Morphology		NA						
Hematology	Erythrocytes		NA						
Hematology	Hematocrit		NA						
Hematology	Lymphocytes Atypical		NA						
Hematology	Lymphocytes/Leukocytes		NA						
Hematology	Monocytes		NA						
Hematology	Monocytes/Leukocytes		NA						
Hematology	Neutrophils Band Form		NA						

Category	Parameter	CTCAE Term	CTC Grading direction: Hypo (L)/ Hyper (H)/ No Grading (NA)	CTC Lab Test Unit	CTC Grade 0	CTC Grade 1	CTC Grade 2	CTC Grade 3	CTC Grade 4
Hematology	Neutrophils Band Form/Leukocytes		NA						
Hematology	Neutrophils/Leukocytes		NA						
Hematology	Reticulocytes		NA						
Hematology	Reticulocytes/Leukocytes		NA						

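### The SAP's Grade 2 hyperphosphatemia cut-off of 1.78 mmol/L lies just above the protocol's 5.5 mg/dL, so the grade of a result of exactly 5.5 depends on an unstated rounding rule; the 5.5 mg/dL summary also contradicts itself at that value

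*SAP*

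**What the plan says.** Protocol 9.1.3 sets its own hyperphosphatemia grades in mg/dL because the toxicity criteria in use do not provide them. The two bands that meet at 5.5 are "Serum phosphate levels > ULN but < 5.5 mg/dL (~ equivalent to Grade 1" and "Serum phosphate levels 5.5 - 6.9 mg/dL (~ equivalent to Grade 2". The next band runs from 7 to 9.9 mg/dL (about Grade 3), and above 10 mg/dL is about Grade 4.

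The grading table in SAP 10.3.3 puts the same scale in mmol/L. Grade 1 is "ULN < aval < 1.78", Grade 2 is "1.78 <= aval < 2.26", Grade 3 is "2.26 <= aval < 3.23", and Grade 4 starts at 3.23. These grades feed the shift table from baseline to the highest post-baseline grade. The section also says that "all laboratory values will be presented in SI units" and pools local with central results. It gives no mg/dL-to-mmol/L factor and no precision for the converted value before it is graded.

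The same section defines a second phosphate output. Its lead-in reads "Summary statistics will be presented for subjects with at least one post-baseline phosphate (phosphorus) level above 5.5", with no unit. The statistic under that lead-in is "Time from start of treatment to Phosphate level of 5.5mg/dL or higher", dated from the first result at or above 5.5 mg/dL.

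**The concern.** The SAP grades are meant to reproduce the protocol's scale in other units. A cut-off rounded upward and paired with an at-or-above sign no longer contains the value it was converted from. For one and the same sample, the protocol would say Grade 2, the shift table Grade 1, and the time-to-5.5 statistic would count an event.

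Hyperphosphatemia matters here. It is named first among the most common adverse events of the Phase I study (Protocol 3.3.2), and 5.5 mg/dL is where the protocol's management table begins (Appendix E). The shift table and the time-to-5.5 summary are the planned laboratory-based descriptions of this toxicity, so they should agree with the protocol's scale and with each other.

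**Working it through.** **Inputs.** Protocol limits: 5.5 and 7 mg/dL (9.1.3). SAP cut-offs: 1.78, 2.26 and 3.23 mmol/L (10.3.3). The conversion factor is not in the documents. I bound it from the SAP's own figures, then use the usual one, 10/30.974 = 0.32285 mmol/L per mg/dL (assumption), with 0.3229 and 0.323 as variants.

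**Reproducing the SAP cut-offs.** 5.5 × 0.32285 = 1.7757; 7 × 0.32285 = 2.2600; 10 × 0.32285 = 3.2285. To two decimals these are 1.78, 2.26 and 3.23, so the SAP figures are correct two-decimal roundings.

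**Which side of 5.5 the cut-off lies on.** Back-converted, 1.78 / 0.32285 = 5.513 mg/dL (5.511 with 0.323), which is above 5.5.

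**The same without an outside factor.** Suppose 2.26 and 3.23 are two-decimal roundings of 7 and 10 mg/dL. The factor in mg/dL per mmol/L then lies within both of these ranges:
- 7/2.265 to 7/2.255, that is 3.0905 to 3.1042
- 10/3.235 to 10/3.225, that is 3.0912 to 3.1008

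The overlap is 3.0912 to 3.1008. Over it, 5.5 mg/dL is between 5.5/3.1008 = 1.774 and 5.5/3.0912 = 1.779 mmol/L, always below 1.78.

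**Applying the SAP rule** (factor 0.32285):

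| Result, mg/dL | mmol/L | Protocol grade | SAP, unrounded | SAP, 3 decimals | SAP, 2 decimals |
|---|---|---|---|---|---|
| 5.4 | 1.7434 | 1 | 1 | 1 | 1 |
| 5.5 | 1.7757 | 2 | 1 | 1 | 2 |
| 5.6 | 1.8080 | 2 | 2 | 2 | 2 |
| 7.0 | 2.25998 | 3 | 2 | 3 | 3 |
| 7.1 | 2.2923 | 3 | 3 | 3 | 3 |

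With 0.3229 and 0.323, 5.5 mg/dL becomes 1.77595 and 1.7765. It is still Grade 1 unrounded or at three decimals, and Grade 2 at two. At 7.0 mg/dL those factors give 2.2603 and 2.2610, which are Grade 3 however rounded. The grade at 7.0 therefore depends on both the factor and the rounding.

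**Results reported in mmol/L to two decimals.** 1.77 × 3.0974 = 5.48 mg/dL (Grade 1 on both scales) and 1.78 × 3.0974 = 5.51 mg/dL (Grade 2 on both). These are not affected at the 5.5 boundary.

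**The 5.5 summary.** Take a subject whose highest post-baseline result is exactly 5.5 mg/dL. The event definition (at or above 5.5 mg/dL) is met. The inclusion condition (above 5.5) is not. No conversion is involved, so no rounding rule resolves it.

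**The case against.** The strongest reply is that the cut-offs are right at the precision at which they are written. If the analysis value is held to two decimals, 5.5 mg/dL becomes 1.78 and is Grade 2, as in the protocol. This is correct, and a reader who infers that every 5.5 mg/dL result will be misgraded goes further than the documents allow. But the SAP does not state that rounding. The decimal rules in SAP 9.1 concern reported summary statistics, not the value compared with a cut-off. Read literally, the rule is applied to the converted value as it stands.

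Other points that stand:
- The protocol scale is itself approximate. It marks its bands as rough equivalents of grades, leaves gaps between 6.9 and 7 and between 9.9 and 10, and does not place exactly 10.
- Management in Appendix E uses mg/dL and is untouched by the SAP table.
- Abnormal laboratory values become adverse events only if the investigator judges them clinically significant (Protocol 9.1.1), so adverse-event grades and shift-table counts need not match in any case.
- The phrase in the 5.5 summary may be loose lead-in wording. It is still the stated inclusion condition, and it conflicts with the event it introduces.

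A reader might also infer that the shift table always understates Grade 2. It does not: if 7.0 mg/dL converts to 2.25998 and is not rounded, a protocol Grade 3 result falls into Grade 2, which overstates Grade 2.

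**Conclusion.** The point holds in a narrow form. The SAP's rule as written departs from the protocol's grade at exactly 5.5 mg/dL unless converted values are rounded to two decimals first, and it is sensitive in the same way at 7 mg/dL. The inclusion phrase of the 5.5 summary contradicts its own event definition whatever the rounding.

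The shift-table effect at 5.5 is confined to results from about 5.50 to 5.51 mg/dL, in practice those reported as 5.5 by a laboratory using mg/dL. It reaches only descriptive safety tables. No hypothesis test, efficacy result or management rule is involved.

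The number of subjects cannot be determined. It would be tempting to assume a distribution for peak phosphate and apply it to the 63 subjects in SAP Table 6. The documents give neither that distribution nor the laboratories' reporting units, and those 63 are the subjects reviewed at the second data monitoring meeting, not the Safety population behind the shift table. The effect could be nil.

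The finding rests on the assumed factor only for the exact decimals. That 5.5 mg/dL lies below 1.78 mmol/L follows from the SAP's own 2.26 and 3.23, if these are roundings of 7 and 10 mg/dL.

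**What to change.** 1. Preferably, grade phosphate on the mg/dL scale with the limits in Protocol 9.1.3, and keep SI units for display. State how values in the gaps between bands, and exactly 10 mg/dL, are assigned, since the protocol does not place them.
2. Alternatively, keep 1.78, 2.26 and 3.23, name one conversion factor, and state that the converted value is rounded to two decimals before comparison. The factor must be named: 5.5 mg/dL rounds to 1.78 only if the factor is no more than 5.5/1.775 = 3.0986 mg/dL per mmol/L, which the usual 3.0974 satisfies.
3. Do not replace 1.78 by 1.776 against unrounded values: 1.7757 is still below 1.776, so 5.5 mg/dL would remain Grade 1.
4. In the phosphate summary of SAP 10.3.3, change the inclusion condition from above 5.5 to at or above 5.5 mg/dL, with the unit.

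The cost is one row or one footnote of the grading table and one phrase. No new data are needed, and no clinical rule changes.
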